Version 6.0	3/28/2011	
Is:
 
10.5 Reporting of Other Second Primary Malignancies
 
All cases of new primary malignancies that occur on PrECOG protocols during or after protocol treatment must be reported as a SAE and documented on a PrECOG SAE form. New primary malignancies should be reported within 24 hours of being aware of diagnosis, regardless of relationship to protocol treatment. SAE submission process described above in Section 10.4 should be followed. A copy of the pathology report should be sent with SAE form, if available.
 
*NOTE:* Data regarding survival and remission status, second primary malignancies, and recurrence of prior malignancies will be followed x 3 years. This should include subjects who may have discontinued the study at any time or for any reason, who may be in a survival follow-up period, or who may have died. Data for all identified cases of subsequently diagnosed second primary malignancies after this 3 year time will be reported voluntarily by the treating physician to the manufacturer.

Version 6.0	3/28/2011	
Was:
 
11.0 Treatment Evaluation
 
Is:
 
11.0 Treatment Evaluation (Response is to be assessed at the end of each treatment cycle within 3 days prior to the start of the next cycle)

Version 6.0	3/28/2011	
11.2 Clarification of Test Indications
 
Was:
 
Listed below are the minimal required tests required to assess response based on the characteristics of their disease at on study.
 
Is:
 
Listed below are the minimal required tests required to assess response based on the characteristics of their disease at on study. Response is to be assessed at the end of each treatment cycle within 3 days prior to the start of the next cycle.

Version 6.0	3/28/2011	
19.7 Electronic Case Report Form (eCRF) Information
 
Was:
 
The completed eCRF must be promptly reviewed, electronically signed, and dated by a qualified physician who is an Investigator or Sub-investigator.
 
Is:
 
The completed eCRF must be promptly reviewed, electronically signed and dated by the Principal Investigator.

Version 6.0	3/28/2011	
Appendix I Informed Consent Example
 
Was:
 
Version Date: November 03, 2010
 
Is:
 
Version Date: March 28, 2011

Version 6.0	3/28/2011	
Appendix I Informed Consent Example
 
Added:
 
Second New Cancers
 
According to researchers, patients with cancer have a higher risk of developing a second new cancer when compared to people without cancer. In clinical studies of newly diagnosed multiple myeloma, a higher number of second cancers were reported in patients treated with induction therapy (treatment as first step to reducing number of cancer cells) and/or bone marrow transplant then lenalidomide for a long period of time compared to patients treated with induction therapy and/or bone marrow transplant then placebo (a capsule containing no lenalidomide). Patients should make their doctors aware of their medical history and any concerns they may have regarding their own increased risk of other cancers.

Version 6.0	3/28/2011	
Appendix I Informed Consent Example
 
What About Confidentiality?
 
Added:
 
A description of this clinical trial will be available on http://www.ClinicalTrials.gov, as required by U.S. Law. This Web site will not include information that can identify you. At most, the Web site will include a summary of the results. You can search this Web site at any time.

Version 6.0	3/28/2011	
Appendix XI Eligibility Checklist
 
Was:
 
NOTE: Phase I Only – Prior to discussing protocol entry with the patient AND prior to registering in IWRS, call PrECOG to ensure that a place on the protocol is open to the patient.
 
Is:
 
NOTE: Phase I Only – Prior to discussing protocol entry with the patient AND prior to registering in eDC, call PrECOG to ensure that a place on the protocol is open to the patient.

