Version 6.0	3/28/2011	
Was:
 
10.3 Adverse events to be graded at each evaluation and pretreatment symptoms/conditions to be evaluated at baseline per Common Terminology Criteria for Adverse Events (CTCAE) Version 4.0 grading unless otherwise stated in the table below:
 
Is:
 
10.2 All Adverse Events are to be graded at each evaluation and all pretreatment symptoms/conditions are to be evaluated at baseline per Common Terminology Criteria for Adverse Events (CTCAE) Version 4.0 grading. The specific Adverse Events/Symptoms in the table below are to be collected as indicated below:
												

Version 6.0	3/28/2011	
Was:
 
10.4 Serious Adverse Event (SAE) Definition
 
A serious adverse event is one that at any dose (including overdose):
 
 ▪ Results in death ▪ Is life-threatening¹ ▪ Requires inpatient hospitalization or prolongation of existing hospitalization ▪ Results in persistent or significant disability or incapacity² ▪ Is a congenital anomaly or birth defect ▪ Is an important medical event³ ▪ Pregnancy 
Is:
 
10.3 Serious Adverse Event (SAE) Definition
 
A serious adverse event is one that at any dose (including overdose):
 
 ▪ Results in death ▪ Is life-threatening¹ ▪ Requires inpatient hospitalization or prolongation of existing hospitalization ▪ Results in persistent or significant disability or incapacity² ▪ Is a congenital anomaly or birth defect ▪ Is an important medical event³ ▪ Diagnosis of a new second primary cancer
-------------	-----------	---

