10.11 Assessment of Attribution

When assessing whether an adverse event is related to a medical treatment or procedure, the following attribution categories are utilized:

Definite: The adverse event *is clearly related* to the investigational agent(s).
Probable: The adverse event *is likely related* to the investigational agent(s).
Possible: The adverse event *may be related* to the investigational agent(s).
Unlikely: The adverse event *is doubtfully related* to the investigational agent(s).
Unrelated: The adverse event *is clearly NOT related* to the investigational agent(s).

10.12 When a study includes both investigational and commercial agents, the following apply:

- When an investigational agent(s) is used in combination with a commercial agent(s), the combination is considered investigational. Reporting of adverse events follows the guidelines for investigational agents.

10.2 All Adverse Events are to be graded at each evaluation and all pretreatment symptoms/conditions are to be evaluated at baseline per Common Terminology Criteria for Adverse Events (CTCAE) Version 4.0 grading. The specific Adverse Events/Symptoms in the table below are to be collected as indicated below:

Category	Adverse Event/Symptoms	Baseline	Each Evaluation
Blood/Bone Marrow	Hemoglobin	X	X
	Neutrophils/Granulocytes (ANC/AGC)	X	X
	Platelets	X	X
Constitutional Symptoms	Fatigue (lethargy, malaise, asthenia)	X	X
Neurology	Neuropathy-Sensory	X	X
Dermatology/Skin	Rash/Desquamation	X	X
Renal/Genitourinary	Cystitis	X	X
Lymphatics	Edema: Limb	X	X
Gastrointestinal	Nausea	X	X
	Vomiting	X	X
	# of stools per day	X	
	Diarrhea		X
Musculoskeletal/Soft Tissue	Muscle Weakness/Lower Extremity	X	X

10.21 Submit via appropriate electronic Case Report Forms (eCRFs) the following AEs experienced by a patient and not specified in Section 10.2. If known, the diagnosis of the underlying illness or disorder should be recorded, rather than individual symptoms. The following information should be documented for all AEs: date of onset and resolution, severity of the event; the investigator's opinion of the relationship to investigational product; treatment required for the AE; cause of the event (if known); and information regarding resolution/outcome.

- Grade 1 and 2 AEs deemed *possibly, probably, or definitely* related to the study treatment or procedure.
- Grade 3 and 4 AEs regardless of attribution to the study treatment or procedure
- Grade 5 AEs (Deaths)

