Time to treatment failure is defined to be the time from registration to the date at which the patient is removed from treatment due to progression, adverse events, or refusal. If the patient is considered to be a major treatment violation or is taken off study as a non-protocol failure, the patient will be censored on the date they are removed from treatment.

Adverse Events: All eligible patients who began treatment will be considered evaluable for assessing adverse event rate(s). The maximum grade for each type of adverse event will be recorded for each patient, and frequency tables will be reviewed to determine patterns. Additionally, the relationship of the adverse event(s) to the study treatment will be taken into consideration. The duration of treatment, dose level and total dose per agent each cycle will also be summarized using descriptive statistics. Lastly, renal function over time will be described using descriptive statistics.

16.38 Pharmacokinetic Analysis:

Pharmacokinetic (PK) analysis will be performed in consented subjects administered a dose during the "Phase II" portion of the trial.

The following pharmacokinetic parameters will be determined using the non-compartmental methods:

- Maximum observed plasma concentration (C_{\max})
- Time to maximum plasma concentration (t_{\max})
- Area under the plasma concentration-time curve from Time 0 to the last measurable time point (AUC)

- Area under the plasma concentration-time curve from Time 0 to infinity (AUC_{∞})
- Apparent total body clearance when dosed orally (CL/F)
- Apparent volume of distribution when dosed orally (V_z/F)
- Terminal elimination half-life in plasma ($t_{1/2,z}$)

The relationship between renal function (CrCl) and PK parameters will be explored.

The results will be summarized by descriptive statistics.

16.4 Data & Safety Monitoring:

Study Monitoring: PrECOG, LLC will be responsible for study monitoring. Refer to Section 19.5 for details.

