## **6.1. Adverse Events**

**Adverse Event (AE)** is defined as any new untoward medical occurrence or worsening of a pre-existing medical condition in a patient administered a medicinal product in a clinical investigation and which does not necessarily have a causal relationship with this treatment. An AE can therefore be any unfavorable and unintended sign (e.g., including an abnormal laboratory finding), symptom, or disease temporally associated with the use of a product (investigational or marketed), whether or not considered related to the product (investigational or marketed). Following written consent to participate in the study, the collection of AEs/SAEs should begin at the initiation of therapy, unless related to a protocol related procedure.

Following written consent to participate in the study, the collection of AEs/SAEs should begin at the initiation of therapy, unless related to a protocol related procedure.

The categories and definitions of severity used for this clinical trial's AEs are defined in the NCI's Common Terminology Criteria (CTCAE) Version 4.0.

Categories 'Definite', 'probable' and 'possible' are considered study drug related. Categories 'not likely' and 'not related' are considered not study drug-related.

AEs should be followed to resolution or stabilization, and reported as SAEs if they become serious.

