### **8.3. Handling of Dropouts or Missing Data**

All attempts will be made to prevent any missing values. Missing or invalid data will be treated as missing, not imputed.

No data imputation will be done for safety parameters except for the adverse events (AEs) with missing starting date. If the AE onset date is unknown, then the date of first study treatment will be used for classification of AEs that were experienced following administration of study drug.

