### **8.7.3. Adverse Events**

Adverse events will be assessed in the safety population.

TEAEs are those that occur after administration of the first study dose until completion of the follow up evaluations. In the case where the start date of the AE is unknown, it will be assumed to be treatment-emergent. Treatment-emergent AEs (TEAEs) will be summarized by system-organ-class (SOC) and preferred term (PT) using the Medical Dictionary for Regulatory Activities (MedDRA®). The frequency of patients who experience TEAEs will be summarized overall cycle. Patients, having the same AE more than once per group, will be counted once for each PT and once within each SOC.

All AEs are listed by patient, including non-treatment-emergent (i.e., pre-dosing or post-dosing) AEs, if applicable. Separate patient data listings are provided for patients who experience treatment-emergent SAEs, TEAEs leading to early termination from the study, or fatal TEAEs.

Additional summary tables will display the number of patients with treatment-emergent AEs by maximum intensity, treatment-emergent AEs by strongest relationship to study drug, and treatment-emergent AEs that led to premature discontinuation of study classified by renal impairment group, system organ class and preferred term. The total number of all treatment-emergent AEs, serious TEAEs, TEAEs by maximum severity, treatment-related TEAEs, TEAEs leading to discontinuations, and TEAEs leading to death will also be summarized by renal impairment group.

CTC Version 4.0 will be used.

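### The treatment-emergent rule in SAP 8.7.3 goes by date alone and ignores the baseline grades collected under Protocol 10.2, so unchanged baseline conditions can be counted as treatment-emergent

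*Protocol*

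**What the plan says.** **Collection.** Protocol Section 10.2 requires: "All Adverse Events are to be graded at each evaluation and all pretreatment symptoms/conditions are to be evaluated at baseline". It adds: "The specific Adverse Events/Symptoms in the table below are to be collected as indicated below". The table marks hemoglobin, neutrophils, platelets, fatigue, sensory neuropathy, rash, cystitis, limb edema, nausea, vomiting and lower-extremity muscle weakness at both time points, 11 items in all. Stool count is baseline only, and diarrhea is post-baseline only.

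**Classification.** SAP 8.7.3: "TEAEs are those that occur after administration of the first study dose until completion of the follow up evaluations". It continues: "In the case where the start date of the AE is unknown, it will be assumed to be treatment-emergent". SAP 8.3 supplies the matching imputation: "If the AE onset date is unknown, then the date of first study treatment will be used for classification of AEs".

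**Definition of an adverse event.** SAP 6.1, like Protocol Section 10.0, requires "any new untoward medical occurrence or worsening of a pre-existing medical condition".

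**Summaries.** SAP 8.7.3 tabulates treatment-emergent events by maximum intensity and by renal impairment group. Protocol 16.37 says: "The maximum grade for each type of adverse event will be recorded for each patient". SAP 8.7.6 calculates change from baseline for laboratory values and counts treatment-emergent graded abnormalities, without defining that term.

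**The concern.** The usual purpose of a treatment-emergent flag is to separate what was present before the first dose from what appeared or worsened afterwards. Here the pre-dose grades are collected, but the flag does not use them. A patient with Grade 1 neuropathy at entry and Grade 1 neuropathy at every later visit has had no treatment-emergent event. If the on-treatment grading becomes an adverse event record dated to that visit, or one with no onset date, the SAP counts it.

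The safety profile is a secondary objective (Protocol 2.22), and Protocol 16.22 plans an exploratory comparison of toxicity profiles among the three renal groups. These are previously treated myeloma patients, all with renal impairment, so baseline abnormalities are to be expected. They need not be equally common across groups. Protocol 1.6, for instance, reports lower baseline platelet counts in relapsed or refractory patients with raised creatinine. Carried-over baseline conditions could therefore blur both the level of toxicity and the contrast between groups.

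**Working it through.** The documents give no figure that depends on this rule, so there is nothing to reproduce. The check applies the rules to the possible cases and then bounds the error.

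**Does any other rule act as a screen?**

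- *Adverse event definition (SAP 6.1, Protocol 10.0).* It screens if the site applies it before creating a record. Protocol 10.2, however, separately orders collection of the listed items at each evaluation, and the SAP does not say how those records are checked against baseline.
- *Submission filter (Protocol 10.21).* It limits Grade 1 and 2 events to those at least possibly related, but only for events not already specified in 10.2. The 11 items lie outside it.
- *Start of collection at initiation of therapy (SAP 6.1).* SAP 8.7.3 nevertheless expects pre-dose records, because it lists non-treatment-emergent events that include them. Only the date separates them from the rest.
- *Laboratory change from baseline (SAP 8.7.6).* It covers hemoglobin, neutrophils and platelets in the laboratory tables. It does not reach fatigue, neuropathy, rash, edema, nausea or weakness, and it does not alter the adverse event tables.

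**Four cases under the rules as written**

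1. Unchanged condition, adverse event definition applied, no record made: not counted. Correct.
2. Unchanged condition, solicited item recorded with an on-treatment date or no date: counted, at its maximum grade. Over-count.
3. Worsened condition, recorded as an event dated at the worsening: counted. Correct.
4. Worsened condition, record keeps its pre-dose onset date: fails the date rule. Under-count.

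Case 2 needs only the collection that 10.2 prescribes plus a record that is not screened. Case 4 needs a dating practice that neither document prescribes.

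**Bound on case 2.** For one item let b be the share of patients with an unchanged baseline abnormality, r the share of the remaining patients with a real new event, and f the share of the unchanged abnormalities that become on-treatment or undated records.

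- Correct rate = (1 − b)r
- Tabulated rate = (1 − b)r + f·b
- Excess = f·b, which runs from 0 (f = 0) to b (f = 1)

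The documents give none of b, r or f. Purely as an illustration of the upper end, with f = 1 and an assumed r of 30%:

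- b = 20%: 0.8 × 0.30 = 24% correct, 24% + 20% = 44% tabulated
- b = 40%: 0.6 × 0.30 = 18% correct, 18% + 40% = 58% tabulated
- b = 60%: 0.4 × 0.30 = 12% correct, 12% + 60% = 72% tabulated

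With r = 10% the tabulated rates are 28%, 46% and 64%, against correct rates of 8%, 6% and 4%. The excess is again 20, 40 and 60 points. It depends on f and b, not on r.

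**Weight of one patient.** At the expected enrolment in Protocol 16.11, the groups have 15 + 15 = 30 (A), 18 + 15 = 33 (B) and 18 + 15 = 33 (C) patients, which sum to the stated 96. One misclassified patient moves a group's rate by 1/30 = 3.3 or 1/33 = 3.0 percentage points.

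**The case against.** The strongest reply is that SAP 8.7.3 classifies adverse events, and an adverse event is by definition new or worsened. On that reading a treatment-emergent event is already a new or worsened one with onset after first dose, which is close to what is asked for. This stands to a considerable degree. A reader might infer that the SAP never compares adverse events with baseline, and the documents do not support that: the definition carries an implicit comparison, and laboratory values get an explicit one.

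A reader might also infer that worsened conditions will be missed. That is not supported either. The worsening is itself the adverse event and occurs on treatment, so it is lost only if the record keeps its pre-dose onset date. A platelet fall would in any case show in the laboratory tables and, in Phase I, in the nadir analysis of Protocol 16.22.

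Three further points are fair. Protocol 10.21 asks for an onset date on all adverse events, so missing dates should be limited. Treating an unknown date as treatment-emergent is a conventional conservative choice. Events are also tabulated by relationship to study drug. Entry conventions may be settled in the eCRF manual or the table templates, which are not part of these documents.

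What remains is that the definition relies on site judgement, while 10.2 orders routine collection. The SAP states no check for the solicited non-laboratory items or for undated records. Conservatism toward unknown dates has no purpose where the same condition is already on file at baseline. Attribution helps the related-event tables but not those by maximum intensity.

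**Conclusion.** The point holds as a gap in the classification rule. As written, SAP 8.7.3 and 8.3 allow an unchanged baseline condition to be counted as treatment-emergent when a solicited item is recorded on treatment or without an onset date. Missed worsening is a lesser risk that depends on how the record is dated.

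The size cannot be computed from the documents. The excess for any item lies between 0 and b percentage points. The upper end assumes that every unchanged abnormality is recorded in this way, which strict use of the adverse event definition would prevent. The illustrative percentages are not estimates for this trial.

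Only descriptive safety tables are affected. A reader might suspect that dose-finding or stopping decisions are affected too, but the documents do not support this. The dose-limiting toxicity criteria (Protocol 7.22) and the stopping rule (Protocol 16.4) have their own definitions and do not use the treatment-emergent flag. The primary endpoint is response.

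**What to change.** In SAP 8.7.3:

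- Define a treatment-emergent event as one that is new after the first dose, or that is higher in CTCAE grade than the pre-dose baseline grade.
- For the Protocol 10.2 items collected at both times, count an item only if the worst post-dose grade exceeds the baseline grade.
- Date a worsening at the grade increase, not at the original onset.
- In 8.7.3 and 8.3, limit the unknown-onset rule to events not already recorded at baseline.
- Add a table of baseline grade by worst post-dose grade for these items, by renal group.

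The cost is a few sentences and minor extra programming, since the baseline grades are already collected. If the SAP is already final, the running note described in SAP 2.1 can carry the change. An item that clears and later returns at its baseline grade would not be counted under this rule, but it would still appear in the by-patient listings wherever it is recorded as an adverse event.

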Appendix VI	Education and Counseling Guidance Document	106
Appendix VII	Lenalidomide Information Sheet.....	109
Appendix VIII	Lenalidomide Days 1 to 21 MEDICATION DIARY	112
Appendix IX	Lenalidomide Every Other Day MEDICATION DIARY	113
Appendix X	Lenalidomide Two Times Weekly MEDICATION DIARY.....	114
Appendix XI	Eligibility Checklist.....	115
Appendix XII	Investigator's Statement.....	118

Schema

PHASE I only: Prior to discussing protocol entry with the patient, call the PrECOG Project Manager to ensure that a place on the protocol is open to the patient. The Project Manager contact information is located in the Study Reference Manual.

If a patient is deemed ineligible or never received treatment, please refer to Section 13.0 for follow-up information.

¹ Cycle = 28 days

² If patient is treated beyond 4 cycles, therapy may be interrupted to allow for stem cell harvest and mobilization (see Section 7.0).

³ Patients must also be treated with anticoagulants (see Section 9.4).

⁴ Refer to Section 7.21 for Dose Escalation Tables

⁵ Dialysis includes hemodialysis or peritoneal dialysis

⁶ When lenalidomide treatment day occurs on a dialysis day, lenalidomide must be taken after dialysis

Generic name: Lenalidomide Brand name(s): Revlimid® Availability: Provided by Celgene	Generic name: Dexamethasone Brand name: Decadron Availability: Commercial
---	---

